1.40	Biomicroscopy	
FDA Slit Lamp Classification Scale will be used to grade the findings and determine eligibility.
 
For the conjunctival redness ██████████ 0.5 unit increments will be used in the grading. Corneal Staining Assessment ██████████ will be graded in 1.0 increments.
 
If any of these slit lamp findings are Grade 3 or higher, the subject will be discontinued. If discontinued a final examination must be completed.
 
If the clearance of the fluorescein needs to be expedited, preservative-free rewetting drops or saline may be instilled.
	████████ ████████ ████████
1.41	Exit VA	Record subjects' distance visual acuity, OD, OS and OU to the nearest letter with their habitual correction in place.	████████
1.42	Instructions	Schedule the subject to return in 7±1 Day for Visit 2	

VISIT 2

Visit 2: Baseline 1			
Step	Procedure	Details	
2.1.	Adverse Events and Concomitant Medications Review	Review the subject's concomitant medications and record any changes from the previous study visit. Record any adverse events or medical history changes from the previous study visit.	████
2.2.	Subject Reported Ocular Symptoms	Subjects will respond to a verbal open-ended symptoms questionnaire.	██████████
2.3.	Visual Acuity	Distance Snellen visual acuity will be measured for each eye with the subject's habitual correction in place. The acuity will be recorded to the nearest letter OD, OS and OU.	██████████
2.4.	Lens Removal (if applicable)	Have the subject remove their habitual lenses and store in an approved storage solution.	
2.5.	Biomicroscopy	FDA Slit Lamp Classification Scale will be used to grade the findings and determine eligibility. For the conjunctival redness ██████████ 0.5 unit increments will be used in the grading. Corneal Staining Assessment ██████████ will be graded in 1.0 increments. If any of these slit lamp findings are Grade 3 or higher, the subject will be discontinued. If discontinued a final examination must be completed. If the clearance of the fluorescein needs to be expedited, preservative-free rewetting drops or saline may be instilled.	██████████ ██████████ ██████████
2.6.	Continuance	Determine whether the subject is eligible to continue in the study based on the examination findings.	

Visit 2: Treatment 3 Lens Fitting			
Step	Procedure	Details	
2.7.	Lens Selection	Assign the study lens based on the randomization scheme.	

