8.2. Withdrawal/Discontinuation from the Study

A subject will be withdrawn from the study for any of the following reasons:

- Subject death during the study period
- Subject withdrawal of consent
- Subject not compliant to protocol
- Subject lost to follow-up
- Subject no longer meets eligibility criteria (eg, the subject becomes pregnant)
- Subject develops significant or serious adverse events causing discontinuation of study lens wear
- Subjects who have experienced a Corneal infiltrative Event (CIE)
- Investigator's clinical judgment regarding the subject safety reasons (that it is in the best interest of the subject to stop treatment)
- Subject not compliant with study lens wear schedule
- Subject not successfully dispensed due to lack of efficacy and safety including poor vision, poor comfort or unacceptable fit

For discontinued subjects, the Investigator will:

- Complete the current visit (scheduled or unscheduled)
- Complete the Final Evaluation, indicating the reason that the subject was discontinued from the study
- Record the spherocylindrical refraction with best corrected distance visual acuity
- Collect used test article(s) (worn or brought to the visit) from the subject and discard them, unless otherwise stated in Section 7.2
- Collect all unused test article(s) from the subject

An additional subject may be enrolled if a subject discontinues from the study prematurely.

In cases where a subject is lost to follow-up, every possible effort must be made to contact the subject and determine the reason for discontinuation/withdrawal. The measures taken to follow up must be documented including two written attempts and a certified letter (or equivalent) as the final attempt.

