14. STATISTICAL METHODS

14.1. General Considerations

All data summaries and statistical analyses will be performed using the SAS software Version 9.4 (SAS Institute, Cary, NC). Throughout the analysis of data, the results for each subject/eye will be used when available for summarization and statistical analysis. Unscheduled visits will be summarized separately and will be excluded from the statistical analysis.

Summary tables (Descriptive statistics and/or frequency tables) will be provided for all baseline variables, efficacy variables and safety variables as appropriate. Continuous variables will be summarized with descriptive statistics (n, mean, standard deviation [SD], median, minimum and maximum). Frequency count and percentage of subjects or eyes within each category will be provided for categorical data.

Summaries will be presented by study lens type and will be performed separately by completion status. All analyses will be conducted on per-protocol population (see Section 14.3).

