14.3. Analysis Populations

Safety Population:

All subjects who were administered any test article excluding subjects who drop out prior to administering any test article. At least one observation should be recorded.

Per-Protocol Population:

All subjects who have successfully completed all visits and did not substantially deviate from the protocol as determined by the trial cohort review committee prior to database hard lock (Per-Protocol Population). Justification of excluding subjects with protocol deviations in the per-protocol population set will be documented in a memo to file.

Intent-to-Treat (ITT) Population:

All randomized subjects regardless of actual treatment and subsequent withdrawal from study or deviation from protocol. At least one observation should be recorded.

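### Section 14.1 puts all analyses on per-protocol completers yet asks for summaries by completion status, and no table uses the defined Safety Population

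*Combined protocol and SAP*

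**What the plan says.** Section 14.1 states that summary tables "will be provided for all baseline variables, efficacy variables and safety variables as appropriate". It then sets two rules in consecutive sentences. The first is "Summaries will be presented by study lens type and will be performed separately by completion status". The second is "All analyses will be conducted on per-protocol population (see Section 14.3".

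Section 14.3 defines three populations:

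- Per-Protocol: "All subjects who have successfully completed all visits and did not substantially deviate from the protocol", with deviations judged by a review committee before the database is locked.
- Safety: "All subjects who were administered any test article excluding subjects who drop out prior to administering any test article", with at least one recorded observation.
- Intent-to-Treat: "All randomized subjects regardless of actual treatment and subsequent withdrawal from study or deviation from protocol", also with at least one observation.

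Section 8.1 does not count a subject as a completer if the subject was discontinued for a reason in Section 8.2. Those reasons include "Subject develops significant or serious adverse events causing discontinuation of study lens wear", a corneal infiltrative event, poor vision, comfort or fit, loss to follow-up and non-compliance. The biomicroscopy steps in Section 7.2 add: "If any of these slit lamp findings are Grade 3 or higher, the subject will be discontinued".

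**The concern.** A safety table should count events among everyone exposed to the product. The per-protocol set is selected after exposure, and part of that selection is the absence of a safety event serious enough to stop participation. If safety tables were built on it, withdrawing events would be missing from the numerator and the withdrawn subjects from the denominator. The table would then look cleaner than the trial was.

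The plan already has the right set and does not use it. A programmer working from Section 14.1 must either follow the per-protocol sentence or follow the completion-status sentence and choose a population without guidance. The two choices give different tables.

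A second difficulty is the instruction to present summaries by lens type, because some safety measurements are not taken lens by lens.

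**Working it through.** There is no plan figure to reproduce, so the check is mainly a comparison of the text.

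**1. Which population each output uses.** Section 14.1 names per-protocol for all analyses. Sections 14.5 and 14.6 (primary and secondary analyses) name no other set. Section 14.7 plans no exploratory analysis. In the available text, neither the Safety nor the Intent-to-Treat Population is assigned to any table or model.

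**2. Whether the two sentences in Section 14.1 can both hold.** Per-protocol requires completion of all visits, so the number of non-completers within it is 0. That leaves two readings:

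- If the analyses referred to include the descriptive tables, a split by completion status has an empty second group, and the sentences contradict each other.
- If they mean only the statistical models, the sentences are compatible, but the safety summaries have no named population.

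Section 14.9 points to the same looseness. It plans multiple imputation when dropout exceeds 15%, which is meant to address dropouts whom a completers-only set does not contain.

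**3. Who would be lost under the literal reading.**

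| Reason for leaving | Source | Wore a study lens? | In Safety Population? | In Per-Protocol? |
|---|---|---|---|---|
| Significant or serious adverse event stopping lens wear, after exposure | 8.2 | Yes | Yes | No |
| Corneal infiltrative event after exposure | 8.2 | Yes | Yes | No |
| Grade 3 or higher at step 1.40 or 2.5 | 7.2 | Yes | Yes | No |
| Grade 3 or higher at step 2.45 | 7.2 | Yes, all five | Yes | Probably not (see below) |
| Unacceptable fit | 7.2, 8.2 | Yes | Yes | No |
| Lost to follow-up after Visit 1 lenses | 8.2 | Yes | Yes | No |
| Substantial deviation | 14.3 | Usually | If exposed | No |
| Grade 3 or higher at step 1.13 | 7.2 | No | No | No |

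Step 2.45 comes after the fifth lens at the last visit. The step says the subject is discontinued, and Section 13.1 lists other Grade 3 or higher corneal findings as significant adverse events. That points to exclusion, but someone could argue that such a subject had completed both visits.

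**4. Size.** Inputs from Section 4.3: about 100 enrolled, 80 targeted to complete.

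- Planned non-completers: 100 − 80 = 20.
- Share of enrolled: 20 / 100 = 20%.

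Consent (step 1.1) comes before the eligibility checks (steps 1.6 and 1.14), and Section 7.2 provides for screen failures at the Final Evaluation. The 20 may therefore include subjects who never wore a study lens. Without a breakdown by reason, the number of exposed non-completers at these targets lies anywhere from 0 (all screen failures) to 20 (none). Completers excluded for deviations would add to it. No point estimate is available.

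**5. Lens type against the examination schedule.**

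- Visit 1: slit lamp before any study lens (step 1.13), then after lenses 1 and 2 (step 1.40).
- Visit 2: slit lamp before lens 3 (step 2.5), then after lenses 3, 4 and 5 (step 2.45).
- No slit-lamp examination is scheduled between lenses. Only an unacceptable fit triggers one.
- Ocular symptoms are taken after every pair (steps 1.26, 1.39, 2.18, 2.31 and 2.44).

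A finding at step 1.40 follows two lens types and one at step 2.45 follows three, so neither can be assigned to a single type. Symptoms can. Scheduled visual acuity with correction in place is taken with the habitual correction (steps 1.9, 1.41 and 2.3), so it too belongs to a visit rather than a lens.

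**The case against.** The strongest reply is the completion-status sentence itself. Section 14.1 speaks of data summaries and statistical analyses as separate things, and it summarises unscheduled visits while keeping them out of the statistical analysis. Safety variables are promised only as summaries. On that reading, per-protocol governs the models, and discontinued subjects appear in their own safety summaries. This is a fair reading, and it defeats any claim that withdrawn subjects are certain to be omitted. It does not repair the plan, because the safety summaries still have no named population. A non-completer group could also mix exposed subjects with those stopped at step 1.13 before any lens, so the split alone does not give a rate among the exposed.

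It is also fair to say that the stakes are limited. This is a non-dispensing handling study with about 15 minutes of wear per pair and no safety endpoint or hypothesis. Section 13.3 requires all adverse events during enrolment to be documented, and Section 13.4 requires them to be reported. What is unsettled is the tabulation set; data capture is unaffected.

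Three stronger inferences are tempting and not supported:

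- That the omitted subjects would be exactly those with adverse events or Grade 3 findings. Fit failures, losses and deviators would go too, and subjects stopped at step 1.13 are outside the Safety Population in any case.
- That 20% of exposed subjects would be missing. This treats all 100 enrolled as exposed, which the documents do not show.
- That slit-lamp findings would be credited to the last lens worn. Nothing in the plan says so. The text shows only that single-lens attribution is impossible, and Section 14.1 does qualify its tables as being provided where appropriate.

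**Conclusion.** The point holds as an internal inconsistency and an unassigned population, and its severity is minor to moderate. Section 14.1 either contradicts itself or leaves the safety summaries without a population. The literal reading gives a safety table conditioned on not having been withdrawn. It would be wrong to conclude that the plan is bound to drop these subjects, because the completion-status sentence allows a reading in which they are shown.

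The number of exposed subjects affected is not computable. At the stated targets there are about 20 non-completers of all kinds, of whom anywhere from none to all could have worn a study lens. The lens-type point stands separately and rests only on the visit schedule.

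The conclusion assumes that no other part of the plan assigns the Safety Population to a table. None does in the available text.

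**What to change.** In Section 14.1:

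1. Limit the per-protocol sentence to the efficacy analyses, and name the set for the Section 14.9 sensitivity analysis, which needs the dropouts.
2. State that adverse events, slit-lamp findings, ocular symptoms and visual acuity are summarised on the Safety Population, with any split by completion status shown within it.
3. Tabulate scheduled slit-lamp findings by visit, and keep lens type for outcomes recorded after each pair, such as symptoms and lens fit. Visual acuity taken with the habitual correction also goes by visit.

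The cost is a few sentences and small changes to table shells. It needs no new data, extra subjects or change to visit procedures, and it does not alter the primary handling analysis.

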14.2. Sample Size Justification

232 cohort subjects from [REDACTED] were used as historical input for the sample size calculation. The lenses used in the above single arm studies had the same optical design as the lenses used in this trial. The standard deviation of CLUE handling from visit 2 and 3 was the input for calculating the sample size.

The true difference between the Test lens and the Control lens was assumed to be 0 and -1 points to make 2 different scenarios. It is reasonable to further assume the handling scores from different lenses are correlated since the only difference in the lenses is the thickness profile (correlation is assumed to be 0.6 and 0.7).

Below is the summary of sample size required to test the primary hypotheses at alpha = 0.05 and power at least 0.8

Mean Diff	Correlation	Actual Power	Sample Size
0	0.6	0.802	116
0	0.7	0.801	87
-1	0.6	0.801	180
-1	0.7	0.800	135

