2.2. Endpoints

To evaluate the handling performance of contact lenses in myopic subjects who are habitual soft contact lens wearers. The primary endpoint will be the subjective handling responses.

Primary Endpoint

The primary endpoint is overall lens handling assessed using the Contact Lens User Evaluation questionnaire (CLUE™). CLUE is a validated Patient Reported Outcome (PRO) questionnaire developed to measure general and throughout the day comfort/vision, as well as symptoms of discomfort/poor vision, lens handling and packaging. Derived CLUE scores using Item Response Theory (IRT) follow a normal distribution with a population average score of 60 (SD 20), where higher scores indicate a more favorable/positive response. A 5 point increase in an average CLUE score translates into 10% shift in the distribution of scores for population of soft contact lens wearers.

Secondary Endpoint

Lens fitting.

Other Observation

Subjective Comfort.

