2.3. Hypotheses

Primary Hypotheses

1. Test lens #1 (30 microns thicker) handling scores will be non-inferior to the Control lens after approximately 15 minutes of wear. A non-inferiority margin of -5 CLUE points will be used.
2. Test lens #2 (16 microns thinner) handling scores will be non-inferior to the Control lens after approximately 15 minutes of wear. A non-inferiority margin of -5 CLUE points will be used.

If both primary hypotheses are met, the following two secondary hypotheses will be tested.

Secondary Hypotheses

1. Test lens #3 (22 microns thinner) handling scores will be non-inferior to the Control lens after approximately 15 minutes of wear. A non-inferiority margin of -5 CLUE points will be used.
2. Test lens #4 (28 microns thinner) handling scores will be non-inferior to the Control lens after approximately 15 minutes of wear. A non-inferiority margin of -5 CLUE points will be used.

Other Hypotheses

Not Applicable.

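### The power of at least 0.8 in Section 14.2 is most likely per contrast; if so, the chance of meeting both primary hypotheses is about 0.69 at the tabulated sizes, and it is lower at the planned 80 completers

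*Combined protocol and SAP*

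**What the plan says.** Section 2.3 sets two primary hypotheses: Test lens #1 (30 microns thicker) and Test lens #2 (16 microns thinner) are each to be non-inferior to Control on the handling score. For each, "A non-inferiority margin of -5 CLUE points will be used". It then says: "If both primary hypotheses are met, the following two secondary hypotheses will be tested". Those secondary hypotheses concern lenses #3 and #4, the two thinnest.

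Section 14.2 presents the "sample size required to test the primary hypotheses at alpha = 0.05 and power at least 0.8". Its inputs are given in the singular: "The true difference between the Test lens and the Control lens was assumed to be 0 and -1 points to make 2 different scenarios". For scores from different lenses the "correlation is assumed to be 0.6 and 0.7". On variability it says only "The standard deviation of CLUE handling from visit 2 and 3 was the input for calculating the sample size", without a value. The table gives 116, 87, 180 and 135 subjects with actual powers of 0.802, 0.801, 0.801 and 0.800.

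Section 14.5 compares each Test lens with Control by its own 95% confidence interval, with a limit of -5. Section 4.3 and the Synopsis plan about 100 enrolled and 80 completers.

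**The concern.** The heading of the table refers to the primary hypotheses together, but each row describes one comparison. Section 14.2 mentions neither two comparisons nor joint power. If 0.80 is the power of one contrast, the probability that both succeed is lower, and that probability decides whether lenses #3 and #4 are tested at all. A reader who takes the table at its word would put the risk of not reaching those tests at about 20%. On the per-contrast reading, with equal true differences, it is about 31% at the tabulated sizes. It is higher at the number of completers the trial plans for.

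**Working it through.** **Inputs.** Margin 5 (Section 2.3). True difference d = 0 or -1, correlation ρ = 0.6 or 0.7, alpha 0.05 with sidedness not stated (Section 14.2). 80 completers (Section 4.3). The SD σ is not printed, so it is solved from the table and is an assumption. The population SD of 20 in Section 2.2 is not named as the sizing input and does not reproduce the table: the calculation below then gives 81, 61, 126 and 95 at one-sided 0.05, or 103, 78, 159 and 120 at one-sided 0.025.

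**Step 1: reproduce the table as one paired contrast.** SD of the difference = σ√(2(1-ρ)). The noncentrality is (5 + d)/(SD of difference/√n). Power comes from the noncentral t with n - 1 degrees of freedom. With σ = 24 and one-sided 0.05:

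| d | ρ | SD of difference | n | SE | Noncentrality | Power at n | Power at n - 1 |
|---|---|---|---|---|---|---|---|
| 0 | 0.6 | 21.47 | 116 | 1.993 | 2.509 | 0.802 | 0.799 |
| 0 | 0.7 | 18.59 | 87 | 1.993 | 2.509 | 0.801 | 0.797 |
| -1 | 0.6 | 21.47 | 180 | 1.600 | 2.500 | 0.801 | 0.799 |
| -1 | 0.7 | 18.59 | 135 | 1.600 | 2.500 | 0.800 | 0.798 |

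All eight printed figures match, for any σ from 23.992 to 24.005. At one-sided 0.025 no σ gives an exact match; about 21.25 comes close, with 116, 88, 180 and 135.

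**Step 2: correlation between the two contrasts.** With a common σ and ρ, Cov(T1 - C, T2 - C) = σ²(1 - ρ) and each variance is 2σ²(1 - ρ). The correlation is 0.5 whatever ρ is.

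**Step 3: probability that both are met, per-contrast reading.** With the same true difference for both lenses, P(both) = Φ₂(z, z; 0.5), where Φ(z) is the power of one contrast. At 0.800 this is 0.687 and at 0.802 it is 0.690, so it is about 0.69 in every row. Simulating three equally correlated scores with paired t limits gives 0.685 to 0.691. This step needs no SD. At a power of 0.80 each, other contrast correlations give 0.64 (correlation 0), 0.67 (0.3) and 0.71 (0.7).

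**Step 4: the Section 14.5 rule.** If the 95% interval is two-sided, each contrast is tested at one-sided 0.025. With σ = 24, power at the tabulated sizes is about 0.70 per contrast and about 0.56 jointly.

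**Step 5: the competing reading.** Suppose the table was built on joint power at one-sided 0.05. Then σ from 21.213 to 21.219 also reproduces all eight figures. At 21.216 the joint powers are 0.802, 0.801, 0.801 and 0.800. The table alone cannot separate the two readings.

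**Step 6: 80 completers, equal true differences.** For row 1 with σ = 24, SE = 21.47/√80 = 2.400 and the noncentrality is 5/2.400 = 2.083. Power is 0.663 for one contrast and 0.51 jointly. All rows:

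| d | ρ | Joint, σ 24, one-sided 0.05 | Joint, σ 21.216, one-sided 0.05 | Joint, σ 24, two-sided 95% | Joint, σ 21.216, two-sided 95% |
|---|---|---|---|---|---|
| 0 | 0.6 | 0.51 | 0.63 | 0.37 | 0.49 |
| 0 | 0.7 | 0.65 | 0.76 | 0.51 | 0.64 |
| -1 | 0.6 | 0.34 | 0.43 | 0.22 | 0.30 |
| -1 | 0.7 | 0.44 | 0.55 | 0.31 | 0.41 |

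**The case against.** The strongest objection is that the SD is not printed and a joint calculation fits just as exactly. On that reading, the statement in Section 14.2 is correct at its tabulated sizes and only its definition of power is missing. This stands: the per-contrast reading is an inference. It is favoured by the single difference per row, the absence of any reference to two comparisons and the round SD of 24.0. None of these is decisive, since an SD estimated from 232 historical subjects need not be round and the singular may be generic.

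The 0.69 also assumes equal true differences. The lenses move in opposite directions (+30 and -16 microns), and Section 1.5 cites handling problems with thin lenses, so lens #1 might do better than lens #2. With σ = 24, one-sided 0.05 and lens #1 at +2, joint power at the tabulated sizes is 0.79 to 0.80. With lens #1 at 0 in the -1 rows it is 0.77. At 80 completers with lens #1 at +2 it is 0.63, 0.75, 0.49 and 0.60; with σ = 21.216 it is 0.74, 0.85, 0.58 and 0.69. One row then exceeds 0.80. This stands as a condition on the figures. Section 14.2 gives no separate difference for each lens, so equal differences are the natural reading of its table.

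The 0.56 depends on σ = 24. With σ = 21.216 and two-sided intervals, the joint figure at the tabulated sizes is 0.69.

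Finally, Section 2.3 uses meeting both primaries only to open the secondary tests. It does not define study success that way, and Section 14.5 concludes on each lens separately. Sizing per contrast is a legitimate choice, provided it is labelled as such.

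**Conclusion.** The point holds in conditional form. Section 14.2 does not say what its power refers to, and the evidence favours power per contrast. On that reading, with equal true differences and a contrast correlation of 0.5, the probability that both primaries are met is about 0.69 at each tabulated size, and about 0.56 under two-sided 95% intervals with SD 24. Under either reading, with equal true differences and one-sided 0.05, joint power at 80 completers is below 0.80 in every row: 0.34 to 0.65 with SD 24 and 0.43 to 0.76 with SD 21.216.

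A reader might infer that the table is an arithmetic error, or that the trial has a 31% chance of failing. The documents support neither. The table is internally consistent under two different calculations, the plan does not equate success with meeting both primaries, and the 31% applies to sizes above the planned number of completers and to equal effects.

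**What to change.** In Section 14.2, state the SD, the sidedness of alpha and whether power is per contrast or joint. If it is per contrast, label the printed powers so. Add the probability that both primary hypotheses are met, at the tabulated sizes and at 80 completers, calculated under the confidence-interval rule of Section 14.5 and with the assumed true difference stated for each of lenses #1 and #2. Describe that probability as the chance that the secondary hypotheses are reached. The cost is an extra table column, a line for 80 completers and a few sentences, and the stated figures will probably look less favourable. No change in enrolment, margin or analysis is asked for.

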4.3. Enrollment Target and Study Duration

Approximately 100 subjects will be enrolled in the study with 80 targeted to complete the cohort. All subjects will have at least -1.00 D to -1.50 D of refractive cylinder in both eyes. The study will take place at several clinical sites and have two study visits per subject.

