14.4. Level of Statistical Significance

All planned analysis for this study will be conducted with an overall type I error rate of 5%.

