14.5. Primary Analysis

Primary efficacy analysis:

The CLUE handling score will be analyzed using a linear mixed model. The model will include the experimental design factors: sequence of lens wear, lens wearing period and lens type as fixed effects. Site and subject nested in site will be included as random effects. Age and gender will be included as fixed covariates when appropriate. The covariance between residual errors from the same subject across lens wearing periods will be selected based on the finite-sample corrected Akaike's Information Criterion (Keselman et al. 1998²). Covariance structures considered may include: Homogenous compound symmetry (CS) and Unstructured covariance structure (UN). The structure that returns the lowest Akaike Information Criteria Corrected (AICC) will be selected as the structure that best fit the data.

Comparisons between each Test lens and Control lens will be carried out using 95% confidence intervals constructed of least-square means (LSM) differences (Test minus Control) from the linear mixed models. Non-inferiority will be concluded if the lower confidence limit is greater than -5 points.

In all models, the Kenward and Roger method (Kenward and Roger, 1997) will be used for the calculation of the denominator of degrees of freedom.

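### The Section 14.2 sample sizes very probably rest on a one-sided 5% test, but Section 14.5 applies a 95% confidence limit; if so, power is about 70%, not 80%

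*Combined protocol and SAP*

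**What the plan says.** Section 14.2 gives four sample sizes "required to test the primary hypotheses at alpha = 0.05 and power at least 0.8". The scenarios combine a true difference of 0 or -1 CLUE points with a correlation between lenses of 0.6 or 0.7. The section does not say whether alpha is one-sided or two-sided. On variability it says only: "The standard deviation of CLUE handling from visit 2 and 3 was the input for calculating the sample size". No value follows.

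Section 14.4 sets an overall type I error of 5%, again without sidedness. Section 14.5 gives the decision rule: "Comparisons between each Test lens and Control lens will be carried out using 95% confidence intervals" and "Non-inferiority will be concluded if the lower confidence limit is greater than -5 points". The margin of -5 is also in Section 2.3. No section mentions a 90% or a one-sided interval.

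On the planned size, Section 4.3 says: "Approximately 100 subjects will be enrolled in the study with 80 targeted to complete the cohort". Section 14.1 bases all analyses on the per-protocol population, so completers are the effective sample.

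**The concern.** A non-inferiority claim uses one limit of the interval. The lower limit of a two-sided 95% interval is a test at one-sided 2.5%. If the sizing used one-sided 5%, the 80% power belongs to a more lenient test than the one in Section 14.5.

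Section 14.2 cannot settle this, because both the sidedness and the SD are absent. The printed powers, given to three decimals, do allow an indirect check, and they point to one-sided 5%.

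Power is the stated basis for the size of the trial. If it is overstated, a comparison that misses the margin may reflect too few subjects and not poorer handling. Section 2.3 opens the secondary hypotheses only if both primary ones are met, so one miss for lack of power closes the sequence.

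**Working it through.** **Inputs.** Margin 5 (Sections 2.3 and 14.5). True difference d = 0 or -1, correlation ρ = 0.6 or 0.7, power at least 0.80 (Section 14.2). Within-subject crossover, hence a paired comparison (Section 5.1). The SD is not printed, so it is back-solved and is an assumption.

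**Formulas.** SD of the paired difference = SD × √(2(1 − ρ)). Noncentrality = (5 + d) × √n / (SD of the difference). Power is the probability that a noncentral t with n − 1 degrees of freedom exceeds the critical value. A fit to the table requires that the smallest n with power of at least 0.80 equals the printed size and that the power rounds to the printed three decimals.

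**Worked example, first row, SD 24.0.** SD of the difference = 24.0 × √0.8 = 21.466. Noncentrality = 5 × √116 / 21.466 = 2.509. The critical value on 115 df is 1.658 at one-sided 5%, giving power 0.8021. It is 1.981 at one-sided 2.5%, giving power 0.701.

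**Reproducing the table.**

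| d / ρ | Printed n (power) | One-sided 5%, SD 24.0 | One-sided 2.5%, SD 21.245 |
|---|---|---|---|
| 0 / 0.6 | 116 (0.802) | 116 (0.8021) | 116 (0.8024) |
| 0 / 0.7 | 87 (0.801) | 87 (0.8007) | 87 (0.8002) |
| -1 / 0.6 | 180 (0.801) | 180 (0.8011) | 180 (0.8021) |
| -1 / 0.7 | 135 (0.800) | 135 (0.8002) | 135 (0.8006) |

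- At one-sided 5%, all eight figures match for SDs from 23.992 to 24.005.
- At one-sided 2.5%, the four sizes match only for SDs from 21.242 to 21.249, and no SD in that range matches more than two of the four powers.
- With df of 2(n − 1), all eight figures match at either level: SD 21.333 to 21.339 at 2.5%, about 24.067 at 5%.
- The only SD printed in the documents is the CLUE population value of 20 (Section 2.2). It does not reproduce the table: power at the tabulated sizes would be about 0.91 at one-sided 5% and 0.85 at one-sided 2.5%.

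**Per-comparison power under the Section 14.5 rule (one-sided 2.5%, df n − 1).**

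| d / ρ | Tabulated n | Power at that n, SD 24.0 | n for 80%, SD 24.0 | Power at 80, SD 24.0 | Power at that n, SD 21.245 | Power at 80, SD 21.245 | Largest SD for 80% power at 80 |
|---|---|---|---|---|---|---|---|
| 0 / 0.6 | 116 | 70.1% | 147 | 54% | 80.2% | 64% | 17.6 |
| 0 / 0.7 | 87 | 69.9% | 111 | 66% | 80.0% | 77% | 20.4 |
| -1 / 0.6 | 180 | 70.1% | 228 | 38% | 80.2% | 46% | 14.1 |
| -1 / 0.7 | 135 | 69.9% | 172 | 48% | 80.1% | 57% | 16.3 |

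**Joint power.** If the table instead gives joint power for both primary hypotheses at one-sided 5% (correlation 0.5 between the two contrasts), an SD of 21.22 yields 0.8022, 0.8005, 0.8011 and 0.8000. The same SD at one-sided 2.5% yields 0.692, 0.689, 0.691 and 0.689.

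**The case against.** Nothing on the page is in open contradiction. Read as two-sided, an alpha of 0.05 in Section 14.2, 5% in Section 14.4 and a 95% interval in Section 14.5 all agree. One-sided 2.5% with an SD near 21.245 returns all four sizes and misses the printed powers by at most about 0.001. The preference for 5% then rests on the third decimal and on assuming n − 1 degrees of freedom. The documents do not state that assumption, and the planned analysis is a five-period mixed model with Kenward-Roger degrees of freedom. An SD taken from 232 historical subjects need not be a round 24.0. The shortfall at 80 completers is visible without any back-solving and is not evidence about alpha. This is also an initial Phase 1 handling evaluation, and type I error is not inflated.

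Much of this stands as a limit on certainty. The one-sided 5% basis is an inference, and the 70% figure must stay conditional. What does not stand is that the text is adequate. If alpha was meant as two-sided, the standard paired-t powers do not match those printed, and a reader has no SD or method with which to resolve it. That 80 is below every tabulated size is indeed a separate fact, but it means that neither reading rescues the power claim at the planned size.

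**Conclusion.** The concern holds, with medium confidence on how the table was built. It very probably used one-sided 5%, whereas the decision rule is one-sided 2.5%. On that basis power at the tabulated sizes is about 70% per comparison, roughly 10 points below the claim. If the table was built at one-sided 2.5%, its sizes are correct and the fault is that the text does not say so while the printed powers point the other way.

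Under either back-solved SD, 80 completers do not reach 80% power in any tabulated scenario under the Section 14.5 rule. The best case is 66% with SD 24.0 and 77% with SD 21.245. An SD of 20, which does not fit the table, would give about 81% in the most favourable scenario (0 / 0.7) and less than 80% in the other three.

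These conclusions assume that the 95% interval is two-sided and that a paired t-test approximates the mixed model. The decision rule itself is sound. This should be fixed before the power statement is relied on.

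**What to change.** Recompute the Section 14.2 table at one-sided 2.5%, to match the 95% interval in Section 14.5. Print the historical SD, the sidedness, the test and degrees of freedom used, and whether power is per comparison or joint for the two primary hypotheses. State the sidedness in Section 14.4 as well. Restate power at the tabulated sizes and at the 80 planned completers. Keep the 95% interval as the decision rule.

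The cost is one power calculation and a short text edit, with no change to conduct. If the table was built at one-sided 5%, the stated power will become less favourable. If it was built at one-sided 2.5%, the sizes stay as they are, but power at 80 completers still has to be reported.
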